1. Demonstrate that the strength of type I IFN signature in psoriatic skin predicts treatment response.

Fifty individuals with moderate to severe psoriasis with high dose etanercept (50mg twice weekly), and the composition of the lesional psoriatic cytokine network will be tracked at the onset (day 0), early (week 2), during the middle (week 6) and at the end of treatment (week 12). Serum samples and PBMC isolation will be done at each time-point for later analyses. Biopsies of uninvolved and lesional skin will be performed before initiation of treatment and then lesional biopsies taken at week 2, week 6 and week 12. Skin will be anaesthetized with 1% lidocaine with epinephrine and 6mm punch biopsies will be taken. Photographs of patients will be obtained and the anatomical location of biopsies recorded. Biopsies will be bisected, with one-half snap frozen in liquid nitrogen and stored at -80° until RNA and protein processing and the other half fixed in 4% formalin for paraffin embedding and immunohistochemistry. Processing will be performed as previously described by our team and only high quality RNA, as determined by Agilent 2100 Bioanalyzer will be used .

Next-generation sequencing of RNA (RNAseq) will be performed on the samples according to Illumina's protocol using 2 $\mu$ g of RNA. Immunohistochemistry will be performed to validate findings with MXA staining used to confirm presence of type I interferon signal. H&E staining will be used to assess the degree of epidermal hyperplasia and response to treatment and immunohistochemical detection of keratin 16, CD3, CD11c, CD163, Ki67 used to validate the degree of histologic response in context of the clinical response. QRT-PCR will be performed for selected gene transcripts to validate the findings of RNAseq.

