**Analysis/Statistics:** RNAseq reads will be mapped using the TopHat algorithm and gene expression levels will be expressed as reads per kilobase of region per million mapped reads (RPKM). Based on prior experience, we estimate that we will obtain around 3 gigabases of sequence for each sample. Inflammation profiles and cytokine signature scores will be calculated as described by our group. Estimating that around 50% of patients will achieve a 75% reduction in Psoriasis Area and Severity Index (PASI) (PASI75) at 12 weeks; this should allow us to determine if effective treatment is associated with complete neutralization of the TNF signal in lesional psoriatic skin and elucidate the effect of the strength of the type I IFN signal on treatment response. For our statistical analyses, we are interested in one outcome variable (PASI score) and two continuous covariates (RNAseq-generated TNF- $\alpha$  signal and IFN- $\alpha$  signal). We anticipate that these data will be analyzed in two ways.

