(2) Second, we will test whether TNF- $\alpha$  and/or IFN- $\alpha$  signals are significantly altered during the course of etanercept therapy, and whether such changes differ between subjects with different PASI response profiles. In these analyses, TNF- $\alpha$  or IFN- $\alpha$  signal will be treated as a response variable in a univariate repeated measures analysis of variance, with subject and time as covariates. In this framework, a shift in TNF- $\alpha$  or IFN- $\alpha$  signal during the course of etanercept treatment will be indicated by a significant time effect. In follow-up analyses, models will include 0-1 covariates indicating specific PASI response profiles (e.g., non-responder, intermediate-responder, or responder), which will allow us to test whether temporal shifts in TNF- $\alpha$  or IFN- $\alpha$  signals differ according to the effectiveness of etanercept treatment (i.e., by evaluating interaction effects involving time and 0-1 covariates denoting PASI response patterns). We anticipate that etanercept treatment will more strongly attenuate TNF- $\alpha$  signals in responders compared to intermediate-responders or non-responders (possibly due to disparities in baseline TNF- $\alpha$  and IFN- $\alpha$  signals). Conversely, we expect that non-responders will be characterized by high IFN- $\alpha$  signals, which remain high during the course of etanercept treatment. All analyses performed using PASI scores will be repeated using physician global assessment scores as the response variable, although we expect results from these two analyses to be consistent. With 50 patients recruited and treated, we estimate that we will have >95% statistical power to detect significant effects in the proposed design (Type I error rate of 0.05). Although the analysis will be primarily focused on TNF and IFN signatures, this dataset will also provide us with opportunities to determine contribution of other inflammatory cellular and cytokine contribution to the clinical response.

**Anticipated Results:** We expect that patients with strong IFN- $\alpha$  signature in psoriatic skin along with weak TNF- $\alpha$  signature will have minimal response to anti-TNF treatment, while patients with the opposite pattern, weak IFN and strong TNF signature, will have significant clinical improvement.

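### Part (2) tests whether the TNF signal changes, so it cannot answer the stated aim of showing complete neutralization; a secondary gap concerns on-treatment IFN level

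*Combined protocol and SAP*

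**What the plan says.** All references are to the combined protocol and SAP.

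- **Aim.** The opening paragraph of Analysis/Statistics says the data should allow the team to "determine if effective treatment is associated with complete neutralization of the TNF signal in lesional psoriatic skin". No reference level or margin is given for complete. Effective treatment could mean PASI75 (expected in about 50%, same paragraph) or the clear-improvement group (about 30%, part (1)).
- **Model.** In part (2) the TNF or IFN "signal will be treated as a response variable in a univariate repeated measures analysis of variance, with subject and time as covariates".
- **Named tests.** A shift in either "signal during the course of etanercept treatment will be indicated by a significant time effect". The plan also asks "whether such changes differ between subjects with different PASI response profiles", which it answers "by evaluating interaction effects involving time and 0-1 covariates denoting PASI response patterns".
- **Expectation for IFN.** Part (2) expects non-responders to have high IFN signals, "which remain high during the course of etanercept treatment".
- **Possible reference tissue.** Under item 1 of Proposed experiments, "Biopsies of uninvolved and lesional skin will be performed before initiation of treatment"; lesional biopsies follow at weeks 2, 6 and 12. No named analysis uses the uninvolved sample. However, "Inflammation profiles and cytokine signature scores will be calculated as described by our group", so the scores may already be referenced to it.

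**The concern.** A time effect says that the mean signal differs between visits. A time-by-profile interaction says that the change differs between response groups. The plan interprets both correctly. Complete neutralization is a statement about what is left at the end of treatment, and neither test measures that. A team following the plan exactly could obtain strongly significant TNF results and still be unable to say whether responders lost some or all of the signal.

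The expectation that non-responders' IFN is high and stays high raises a smaller version of the same issue. Level is tested at baseline in part (1). On treatment, a constant gap between response groups produces neither a time effect nor an interaction.

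**Working it through.** **The plan's own figure.** The plan states more than 95% power with 50 patients at a Type I error of 0.05. It gives no effect size, SD, correlation, sidedness or target test, so the figure cannot be reproduced, and it is not attached to any test of level.

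**Inputs from the plan.** N = 50; response groups 30/40/30%, i.e. 15 non-responders, 20 intermediates and 15 responders; about 25 patients if PASI75 defines response; visits at days 0, 14, 42 and 84.

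**Assumptions (not in the plan).** Visit correlation 0.8–0.9 per 14 days; 0, 25 or 50% independent biopsy noise; SD constant, falling to 0.6 or rising to 1.6; baseline TNF excess L = 2–3 SD over uninvolved skin; 50/80/100% of the fall reached by weeks 2/6/12. Tests are two-sided.

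**1. Do the named tests separate partial from complete TNF loss?** (simulation, Greenhouse-Geisser corrected)

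| Loss in responders / intermediates / non-responders | Time effect significant | Interaction significant |
|---|---|---|
| 60/30/0%, constant SD | 83–100% | 48–100% |
| 60/30/0%, all SD patterns | 57–100% | 27–100% |
| 100/30/0%, all SD patterns | 87–100% | 75–100% |

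In one fixed setting (responders only, L = 2 SD, correlation 0.5), removing half the excess gives a significant time effect in 91% of trials with 15 patients and 99.7% with 25. Removing all of it gives 100%. Significance is likely either way.

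**2. A residual test.** For each responder take D = (week-12 lesional − baseline uninvolved) − f × (baseline lesional − baseline uninvolved). Claim a residual below f if the upper end of the two-sided 95% CI for mean D is below 0. Under full neutralization mean D = −fL. With constant lesional SD 1,

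Var(D) = 1 + f² + (1−f)²u² − 2fr − 2(1−f)²uc,

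where u is the uninvolved SD (0.5–1), c its correlation with lesional skin (0–0.3), and r the baseline to week-12 correlation (0.13–0.53). Power comes from the noncentral t with n−1 df and noncentrality fL√n / SD(D).

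- Worst case, f = 0.25, n = 15, L = 2, u = 1, c = 0, r = 0.13: Var = 1 + 0.0625 + 0.5625 − 0.065 = 1.56; SD 1.249; noncentrality 0.5 × 3.873 / 1.249 = 1.55; power 30%.
- Best case, L = 3, u = 0.5, c = 0.3, r = 0.53: Var = 1 + 0.0625 + 0.1406 − 0.265 − 0.1688 = 0.769; SD 0.877; noncentrality 0.75 × 3.873 / 0.877 = 3.31; power 87%.

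| Limit f | 15 responders | 25 responders |
|---|---|---|
| 25% | 30–87% | 49–98% |
| 33% | 50–99% | 74–100% |
| 50% | 87–100% | 98–100% |

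A loose limit does not mean complete. With f = 0.5, a true residual of 20% and n = 15, the worst-case noncentrality is (0.5 − 0.2) × 2 × 3.873 / 1.170 = 1.99. The claim is then already made in about 46% of trials, and more often in the other settings.

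The CI half-width for the residual share of the baseline excess is 18–39% with 15 patients and 13–29% with 25 (constant SD).

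**3. Constant IFN gap.** Let non-responders lie 1 SD and intermediates 0.5 SD above responders at every visit. The corrected time test rejects in 4.5–5.1% of trials and the interaction in 4.5–5.3%, which is the false-positive rate. A contrast of mean week 2/6/12 IFN (15 v 15, 47 df) has noncentrality 1 / √(V × 2/15), where V is the variance of the three-visit mean. At correlation 0.9 without noise, V = 0.807, noncentrality 3.05, power 85%. At 0.8 with 50% noise, V = 0.498, noncentrality 3.88, power 97%. With rising SD the range is 57–81%; with falling SD it is 97% or more. The baseline contrast alone has 76%.

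**4. Sphericity.** With no true effect, uncorrected 5% tests run at 5.0–6.8% with 25–50% biopsy noise and 6.5–8.5% with none. Greenhouse-Geisser gives 4.4–5.4%.

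**The case against.** The strongest reply is that part (2) asks only whether signals change and whether change differs by response, and its tests answer exactly that. Its operative TNF prediction is stronger attenuation in responders, which the interaction tests. This is right for part (2), but the neutralization aim is still stated in the introduction to the same section and no other analysis addresses it.

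That a significant change does not prove completeness is true by definition. The simulation ranges pool different covariances, and their overlap is not the proof. This stands: the figures show only how often the ambiguous result would occur.

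On IFN much of the reply stands.

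- The statement is an expectation, not a formal aim.
- Part (1) tests the baseline level.
- If IFN falls in responders and not in non-responders, the named interaction can detect it: power is 34–66%, 71–97% and 94–100% for responder falls of 1, 1.5 and 2 SD (intermediates half that, constant SD).
- The 0-1 covariates imply a group main effect.

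A reader might infer that on-treatment IFN level cannot be tested at all, because group is aliased with subject. That holds only if subject is a fixed effect (design rank 53 before and after adding the group terms). The plan does not say so, and a repeated measures ANOVA with groups ordinarily has a between-subject stratum. What remains is that the main effect is not named and averages baseline with on-treatment visits.

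A reader might also infer that the conclusions would be drawn by eye. Nothing in the plan says this.

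**Conclusion.** The point holds in a limited form and is minor. As written, the plan cannot answer its aim of complete TNF neutralization: both named tests concern change, complete and effective are undefined, and no residual is tested. This needs no assumption. The 83–100% and 48–100% figures rest on assumed effects and covariances. If scores are already referenced to uninvolved skin, a residual test is still missing.

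The IFN gap is secondary: a persisting constant difference is picked up by neither named part (2) test, but baseline level and diverging change are covered. The sphericity inflation, to about 5–9%, is small and easily removed.

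It would be wrong to read this as undermining the trial's main hypothesis. Whether baseline IFN predicts response is tested in part (1), which does not depend on any of these tests.

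**What to change.** 1. **TNF (main change).** Either reword the aim to attenuation, or define neutralization before the data are seen. For the second option, state the responder group and a strict limit f, and use the rule in step 2 of the working: upper end of the two-sided 95% CI (equivalently a one-sided 97.5% limit) below 0. If scores are already referenced to uninvolved skin, test the residual score directly. Report the residual share with its CI. If f is loose, such as 50%, call the result residual below f, not complete.
2. **IFN.** State that subject is random or has its own between-subject stratum. Name the non-responder v responder contrast of mean week 2/6/12 IFN as a test of a persisting gap. That contrast does not show that IFN stays high, since both groups could fall equally, so also report non-responders' change from baseline with a 95% CI.
3. **Error rate.** Apply a Greenhouse-Geisser correction, or use a mixed model with visit as a factor.

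**Cost.** Analysis text only; every biopsy needed is already planned. The correction loses a little power, or the mixed model adds a few covariance parameters. Uninvolved skin is sampled only at baseline, so it is a fixed reference. With about 15 responders a 25% limit may be out of reach (30–87% power), in which case attenuation is the honest wording.

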The clinical evidence supporting this phenomenon has grown over the past few years. The induction or exacerbation of psoriasis during anti-TNF therapy, which has now been reported in several hundred patients (9, 10) is one such example, and may occur in patients treated for inflammatory conditions other than psoriasis. The psoriatic lesions of these patients have a greatly increased type I interferon signal, as determined by increased tell-tale Myxovirus Resistance Gene A (MxA) expression, compared with control psoriasis samples and similar observations have been made in patients exposed to the Toll-like receptor (TLR)-7 agonist imiquimod. Imiquimod is a very effective inducer of type I interferon production by pDCs (15) and has been shown to exacerbate psoriasis both at the treated area as well as distant skin sites. Similarly, to anti-TNF exacerbated psoriasis, this reaction is accompanied by influx of pDCs and increased MxA expression. Interestingly, but in line with the observations above, this reaction appears to be exacerbated in patients on anti-TNF treatment. This cross-regulation is likely to extend beyond psoriasis as diseases characterized by increased type I IFN signal are frequently exacerbated or triggered by TNF treatments, including lichenoid skin reactions and the increased frequency of positive anti-double stranded DNA antibody titers and less commonly clinical systemic lupus erythematosus, which are both reversible upon discontinuation of treatment.

We have demonstrated that the inflammatory and cytokine network in chronic plaque psoriasis is heterogenous with large variation in the strength of the type I

IFN- $\alpha$  and TNF- $\alpha$  signals between different patients. Thus, about 35-40% of patients show an enriched IFN- $\alpha$  signature in lesional psoriatic skin, which, perhaps coincidentally, is around the same ratio of patients showing limited response to etanercept therapy. Our analysis of a small cohort of patients (n=15) treated with etanercept indicated that those patients with increased IFN- $\alpha$  signal had poorer response to therapy and that the strength of the IFN- $\alpha$  signal was the main predictor of treatment response.

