These observations form the basis of our hypothesis **that the balance between type I IFN and TNF determines the response to anti-TNF treatment**. The goal of the proposed study is to address this hypothesis and demonstrate that the strength of the type I IFN signature in psoriatic skin is the major determinant of the clinical response to anti-TNF treatment.

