(1) First, we will test whether temporal change in PASI score is significantly associated with baseline TNF- $\alpha$  signal, baseline IFN- $\alpha$  signal, and/or an interaction between these two baseline signals. Along these lines, a cumulative score reflecting change in PASI during the course of etanercept treatment will be calculated for each patient. This score will then be treated as a continuous response variable, and we will use robust linear modeling to test whether scores are significantly associated with baseline TNF- $\alpha$  signal, baseline IFN- $\alpha$  signal, and/or an interaction between these two signals. In addition, we expect that it will be possible to unambiguously classify 30% of patients as non-responders, with an equal percentage showing clear improvement in PASI score, and the remainder showing an intermediate response. Accordingly, we will also categorize patients according to improvement in PASI score (i.e., responders, intermediate-responders, and non-responders), and use cross-validation to calculate AUC statistics to directly quantify the capacity of baseline TNF- $\alpha$  and IFN- $\alpha$  signals to predict patient response status. Based upon preliminary data ( $n$  = 15 patients), we anticipate that improved PASI score will be associated with a heightened baseline TNF- $\alpha$  signal and weakened baseline IFN- $\alpha$  signal. The proposed study design will allow us to not only confirm this expectation, but will provide increased power to assess a possible TNF- $\alpha$ /IFN- $\alpha$  interaction effect, and to better characterize quantitative thresholds associated with response and non-response.

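### The >95% power figure names no test or effect size, so it is not shown to apply to the planned tests, and no primary term is chosen among the three baseline terms

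*Combined protocol and SAP*

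**What the plan says.** The only power statement closes part (2) of Analysis/Statistics: "With 50 patients recruited and treated, we estimate that we will have >95% statistical power to detect significant effects in the proposed design", with a Type I error rate of 0.05.

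The design it refers to contains several kinds of test. Part (1) defines the outcome: "a cumulative score reflecting change in PASI during the course of etanercept treatment will be calculated for each patient". It regresses that score, by robust linear modelling, on baseline TNF signal, baseline IFN signal, "and/or an interaction between these two baseline signals". It adds a cross-validated AUC for response status and says the design "will provide increased power to assess a possible" TNF/IFN interaction. Part (2) tests for change over time in each signal by repeated-measures ANOVA, then compares response groups by "evaluating interaction effects involving time and 0-1 covariates denoting PASI response patterns". The PASI analyses are repeated with the physician global assessment.

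The aim is stated more narrowly. Aim 1 reads "Demonstrate that the strength of type I IFN signature in psoriatic skin predicts treatment response", and Rationale and Hypothesis says the IFN signature "is the major determinant of the clinical response to anti-TNF treatment". That section reports from 15 earlier patients that the IFN "signal was the main predictor of treatment response", but gives no coefficient, correlation or variance. The other nearby figures, about 50% reaching PASI75 and 30% clear non-responders with the same share of clear improvers, are response rates. They are not effect sizes for either signal.

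**The concern.** A power figure belongs to a particular test, at a particular effect size and significance level. Here one figure stands for a whole family of tests with none of those inputs given. A reader cannot tell which effects the study could miss, or how much weight a null result would carry.

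The same gap affects the error rate. Three baseline terms are joined by and/or, no primary term is named and no multiplicity rule is given, so it is unclear which result would count as confirming the hypothesis.

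A third issue follows from fitting main effects and interaction together. Unless the signals are centred, the IFN coefficient is the IFN effect at a TNF signal of zero, which may be far from any observed patient. Its power can then be much lower than that of the average IFN effect.

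**Working it through.** **Inputs from the plan.** n = 50; Type I error 0.05; a linear model with three terms (IFN, TNF, interaction), hence 50 − 4 = 46 residual df. Effect size, SD, within-subject correlation and sidedness are not given.

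**Reproducing the plan's figure.** This is not possible, because there is no effect size to enter. The check therefore runs the other way: what effect gives 95% power?

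**One main-effect term, least squares.** With f = r/√(1 − r²), the noncentrality with fixed predictors is f√n. For random predictors, f² is multiplied by a chi-square variable on n − 3 = 47 df and the power is averaged over it.

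| Predictors | Test | r for 80% power | r for 95% power |
|---|---|---|---|
| Fixed | one-sided | 0.336 | 0.427 |
| Fixed | two-sided | 0.375 | 0.462 |
| Random | one-sided | 0.351 | 0.450 |
| Random | two-sided | 0.391 | 0.487 |

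Example (fixed, two-sided): r = 0.462 gives f = 0.521 and noncentrality 0.521 × 7.071 = 3.68. The critical t is 2.013, so power is roughly Φ(3.68 − 2.01) = Φ(1.67) ≈ 95%.

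Two-sided power (fixed/random) is 59%/55% at r = 0.30 and 86%/82% at r = 0.40. The 0.30 and 0.40 are illustrative, not from the plan.

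**Robust fit.** If the robust fit has 95% efficiency (assumed), the two-sided random-predictor thresholds become 0.496 for 95% power and 0.400 for 80%.

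**Fewer evaluable patients.** Only high-quality RNA will be used and no loss rate is given. With 45 or 40 evaluable (assumed), the two-sided 95% threshold is 0.51 or 0.54 (random), or 0.48 or 0.51 (fixed).

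**Interaction.** Simulation with normal signals at n = 50 gives about 51% two-sided power at partial r = 0.30 and about 95% at 0.54–0.55, for assumed IFN–TNF correlations of 0, −0.4 and 0.5. With uniform, independent signals, 95% is reached at about 0.50.

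**Three terms joined by and/or.** If each is tested at 0.05, all are null and any one may support a claim, independence gives 1 − 0.95³ = 1 − 0.857 = 14.3%. Simulation of the correlated tests gives about 13–14%.

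**Uncentred interaction.** Assume independent signals with means 3 SD above zero, no true interaction, and IFN partial r = 0.487 (f = 0.558). Centred, the noncentrality is 0.558 × 7.07 = 3.94. Uncentred, the variance of the IFN coefficient rises by about 1 + 3² = 10, so the noncentrality falls to 3.94/√10 = 1.25 and power to about Φ(1.25 − 2.01) = Φ(−0.76) ≈ 22%. Simulation gives about 94–95% centred and 21–22% uncentred.

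**The case against.** The best defence is that >95% is a lower bound. It could hold for every formal test if the effects are large, and the plan expects a large IFN effect. That stands. A partial correlation of 0.487 means the signal explains about 24% of the remaining variance (0.487² = 0.237), which is not implausible for a main determinant of response. A reader might infer that the figure is wrong, or that one figure cannot hold across such different tests. The documents support neither reading; they show only that the figure lacks a stated basis.

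A reader might also infer that the plan promises 95% power for the interaction. The remark about increased power follows directly on the 15-patient data and most naturally compares 50 patients with 15, which is plainly true. Whether the >95% sentence covers the interaction is unclear, and the interaction thresholds depend on the assumed signal distribution.

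Nor is 13–14% the plan's error rate. The plan does not say that each term is tested at 0.05, or that any one suffices. Aim 1 points to IFN, and expected directions are stated for both signals. What stands is that no primary term is named and no rule keeps the overall error at 0.05.

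Finally, baseline PASI adjustment is not needed to repair a power sentence, and the cumulative score, which is undefined, may already be relative to baseline. That is fair. The adjustment is recommended because the outcome is a change in PASI and may depend on its starting value.

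**Conclusion.** The point holds in limited form and should be fixed. The power statement is unsupported, not refuted. For one baseline main effect it requires a partial correlation of at least about 0.43 (one-sided, fixed predictors) to 0.49 (two-sided, random predictors), assuming least squares and 50 complete cases. A moderate effect of 0.30 would be missed in roughly 41–45% of such studies under a two-sided test. The interaction is harder to detect if the signals are normal, so a null interaction should not be read as a 95%-powered negative unless the true effect is large.

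The loss of error control is conditional on how claims are made. The loss of power from an uncentred interaction is conditional on the scale of the scores: the drop to about 21–22% rests on the assumed 3 SD offset, and it disappears if the signature scores are already centred. The plan does not say whether they are.

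**What to change.** 1. Name one primary test in line with aim 1: the baseline IFN coefficient for the cumulative PASI-change score in the robust linear model, two-sided 0.05. Include baseline TNF and baseline PASI as covariates, and either omit the interaction or centre both signals. Baseline PASI is already in the visit flow chart.

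2. Label the TNF, interaction, time, time-by-response-group, AUC and physician global assessment analyses secondary.

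3. Replace the power sentence with wording such as: *With 50 evaluable patients, the primary two-sided test has 95% power for a partial correlation of about 0.49 and 80% power for about 0.39 (least squares, random predictors), or about 0.50 and 0.40 if the robust fit has an assumed 95% efficiency.* Make no blanket power claim for the secondary tests.

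The cost is a less favourable power statement, one added covariate, and secondary tests that can no longer carry a primary claim. No patients, visits or samples are added.
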